## 7.2 Sample Size/Power and Trial Duration

A maximum of 59 patients may be enrolled, in order to accrue 56 evaluable patients, assuming that the attrition rate (i.e., missing patient symptom diary at 3 weeks) will be at most 5%. With 56 evaluable patients, there will be 80% power for a chi-square test at one-sided 5% type I error, to test the null hypothesis that the rate of moderate to severe lethargy at 3 weeks is  $\geq 35\%$  versus the alternative hypothesis that the rate is  $\leq 20\%$ . To complete accrual for the phase II portion of the trial, the entire trial should be active for six years.

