## 3 Subject Selection and Withdrawal

### **3.1 Accrual**

This study plans to enroll 56 evaluable patients over 72 months. The University of Pennsylvania, Penn satellites, Walter Reed National Military Medical Center, other affiliated Department of Defense (DOD) hospitals, and Massachusetts General Hospital (MGH), see in excess of 20 patients with stage I, IIA, and IIB testicular seminoma per year. Of the patients with seminoma treated annually at these participating institutions, we would reasonably expect to accrue 8 to 10 patients on study annually. Only MGH and the University of Pennsylvania will be treating patients with protons. The Walter Reed National Military Medical Center/Department of Defense affiliates will be referring patients to the University of Pennsylvania.

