## 6.2 Evaluation and Follow-up

6.2.1 Timing of Assessments: all subjects will be evaluated prior to initiation of treatment, weekly during the course of the primary protocol study treatment period and for eight weeks following the completion of proton beam radiation therapy, and 90 days following the start of radiation therapy by the treating radiation oncologist. Patients will be evaluated every three months during the first year following radiation therapy, approximately every six months during the second year following therapy, and annually for years three to five following therapy. Effort will be made to follow subjects beyond five years to assess for toxicity related to radiation treatment and survival, either by the treating radiation oncologist or a referring physician.

6.2.2 Pre-treatment: after determining eligibility, pre-treatment patient assessment will include history and physical examination, performance status assessment (Appendix C), toxicity assessment (as

per protocol section 6.2.5), and quality of life assessment with EORTC QLQ-C30 (Appendix D), Testicular Cancer Patient Diary Card (Appendix E), and EuroQol EQ-5D (Appendix F). Patients will also undergo pre-treatment laboratory evaluation to include complete blood count, semen analysis, follicle-stimulating hormone level, luteinizing hormone level, testosterone, and serum creatinine or creatinine clearance. **Patients who object to the semen analysis or are not covered by their insurance company to have the analysis will not be excluded from the study. If the semen analysis is performed, an optional DNA fragmentation will also be performed from the semen analysis if covered by the patients insurance. This portion of the analysis will only be performed at the Coordinating Center, University of Pennsylvania, and not at participating sites.**

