#### 7.1.2 Endpoints

- Acute Toxicity is defined as any Grade 3 or higher non-hematologic toxicity that occurs within 90 days following the start of proton therapy. NCI Common toxicity criteria (CTC Version 4.0) grades will be employed (Appendix A).
- Late Toxicity is defined as any Grade 3 or higher non-hematologic toxicity that occurs beyond 90 days following the start of proton therapy. NCI Common toxicity criteria (CTC Version 4.0) grades will be employed (Appendix A).
- Clinical Efficacy: Time to local failure will be defined as the time from the start of radiation therapy to local failure. Time to distant failure will be defined as the time from the start of radiation therapy to distant failure. Relapse-free survival will be defined from the time from the start of radiation therapy to any failure or death. Cause-specific survival will be defined from the time from the start of radiation therapy to death due to seminoma. Overall survival will be

defined from the time from the start of radiation therapy to death due to any cause or last patient follow-up. These outcomes will be summarized at the end of the phase II study.

- Quality of Life Measures: EORTC QLQ-C30, Testicular Cancer Patient Diary Card, and EuroQol EQ-5D will be evaluated at multiple times during and post-radiation. We hypothesize that compared to baseline, quality of life measures will worsen during and immediately post-radiation and will then gradually improve after radiation. These deficits are expected to be less than those seen for photon treated patients and the time course to return to baseline should be shortened. These outcomes will be summarized at the end of the phase II study.
- Moderate to Severe Lethargy will be scored on the Testicular Cancer Patient Diary Card (Appendix E). The rate of moderate to severe lethargy at week 3 will be evaluated. This outcome will be summarized at the end of the phase II study.

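### The 72-month study duration covers accrual only, and the end of study at which efficacy and quality of life are summarised is not otherwise defined, although each patient has five years of scheduled follow-up

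*Combined protocol and SAP*

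**What the plan says.** Three places give the same length of time:

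- The Study Summary lists a study duration of 72 months.
- Section 3.1 gives 72 months as the enrolment period: "This study plans to enroll 56 evaluable patients over 72 months".
- Section 7.2, whose heading covers trial duration, ties the active life of the trial to accrual: "To complete accrual for the phase II portion of the trial, the entire trial should be active for six years".

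Section 3.1 also gives the expected rate: "we would reasonably expect to accrue 8 to 10 patients on study annually". Section 7.2 sets the numbers: "A maximum of 59 patients may be enrolled, in order to accrue 56 evaluable patients".

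Follow-up runs much longer. Section 6.2.1 has visits every three months in year 1, about every six months in year 2, and "annually for years three to five following therapy". Section 6.2.6 collects late adverse events for up to five years. Section 6.2.7 adds toxicity inquiries in years 5 to 15.

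For the efficacy and quality-of-life outcomes, 7.1.2 says: "These outcomes will be summarized at the end of the phase II study". The lethargy item has the same timing. The acute- and late-toxicity items have no reporting date. Section 7.1.4 specifies cumulative incidence for local and distant failure and Kaplan-Meier for relapse-free, cause-specific and overall survival. For toxicity it specifies rates with 95% confidence intervals and does not mention unequal follow-up.

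**The concern.** A trial whose whole stated duration is its accrual period leaves essentially no follow-up for its last patients, while the visit schedule requires five years for each of them. The two statements need reconciling.

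The date of the secondary analyses depends on the answer. The only duration the documents give is 72 months, so a reader looking for the end of the study will naturally land there. An analysis at that point would have little information at the later visits. The late-toxicity rate, computed as a simple proportion, would mix patients followed for weeks with patients followed for years. Late complications are a secondary objective (2.3.3), and a proportion that is too low errs in favour of the treatment.

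**Working it through.** **The plan's own figures.** For a one-sample test of 35% against 20%, one-sided 5%, 80% power (7.1.4, 7.2):

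n = [(1.645 × √(0.35 × 0.65) + 0.842 × √(0.20 × 0.80)) / 0.15]² = 55.87, rounded up to 56.

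Power at 56 is 80.1%. Enrolment is 56 / 0.95 = 58.9, rounded up to 59. All three agree with 7.2, so the difficulty is not in the sample size.

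**Time to accrue** = patients / annual rate × 12, using the 8 to 10 per year in 3.1:

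| Rate per year | 56 patients | 59 patients |
|---|---|---|
| 10 | 67.2 months | 70.8 months |
| 9 | 74.7 months | 78.7 months |
| 8 | 84.0 months | 88.5 months |

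Finishing in 72 months needs 56 / 6 = 9.3 or 59 / 6 = 9.8 patients per year, the upper part of the stated range. At 8 per year, 8 × 6 = 48 patients are enrolled by month 72.

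**Follow-up available at month 72.** Assume uniform accrual over A months and no loss to follow-up. The expected number with at least f months is N × (72 − f) / A, capped at N.

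| Scenario | ≥ 24 months | ≥ 36 months | ≥ 60 months |
|---|---|---|---|
| 56 over 72 months | 37.3 | 28.0 | 9.3 |
| 10 per year (56 over 67.2 months) | 40.0 | 30.0 | 10.0 |
| 8 per year (48 enrolled by month 72) | 32.0 | 24.0 | 8.0 |

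In the first scenario, the share with five years is 12 / 72 = 1/6, so about 47 of 56 lack it. Median potential follow-up is 72 / 2 = 36 months.

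**Time for every patient to reach five years** = accrual + 60 months: 72 + 60 = 132. The range runs from 67.2 + 60 = 127.2 to 88.5 + 60 = 148.5. This excludes the inquiries in years 5 to 15.

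**Effect on a crude late-toxicity rate (illustration).** The documents give no late-toxicity risk, so assume a true five-year risk of 10%, constant hazard, uniform entry over six years, no losses, collection capped at five years, and ignore the 90-day exclusion.

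- Hazard: λ = −ln(0.90) / 5 = 0.0211 per year.
- Expected crude proportion at month 72: (1/6) × [∫₀⁵ (1 − e^(−λt)) dt + 1 × 0.10] = (1/6) × [(5 − 0.10 / λ) + 0.10] = (1/6) × [0.254 + 0.10] = 0.059.

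A true 10% would appear as about 5.9%, roughly 40% too low in relative terms.

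**Effect on the short-term endpoints.** With 56 patients over 72 months (about 2,190 days), the expected number short of day 21 at month 72 is 56 × 21 / 2,190 = 0.5. The expected number short of day 90 is 56 × 90 / 2,190 = 2.3.

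**The case against.** The best defence is that 72 months is simply the enrolment period, mislabelled as study duration in a one-line summary. Section 7.2 ties the six years to completing accrual, and active can be read as open to enrolment. Nothing says follow-up stops at month 72: 6.2 schedules visits to year 5, and 3.6 follows withdrawn subjects for survival for at least five years. This may well be what was intended. It does not remove the problem, because the documents never say so and give no other meaning to the end of the study.

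Several stronger readings are tempting, and the documents do not support them:

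- **That five-year late-toxicity and relapse results cannot exist at the time of analysis.** Patients enrolled in roughly the first year (8 to 10) would reach five years by month 72, and the methods in 7.1.4 for failure and survival accept staggered entry and censoring.
- **That a planned five-year endpoint is lost.** No five-year rate is named in 7.1.2 or 7.1.4. Five years is the visit schedule and the adverse-event collection window.
- **That late toxicity will be missing when it falls due.** The late-toxicity item in 7.1.2 carries no reporting date.
- **That the primary endpoint is compromised.** It needs 21 days of follow-up, 3.1 counts evaluable patients, and the acute-toxicity rule in 7.1.3 counts only patients followed for 90 days. At most a few late entrants are affected.
- **That accrual uses exactly 72 months.** At 10 per year it ends a little earlier; at 8 or 9 per year it overruns.

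**Conclusion.** The stated duration equals the accrual period and does not fit the plan's own five-year follow-up schedule. The end of the phase II study, on which the efficacy and quality-of-life summaries depend, has no other definition.

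If month 72 is the analysis date, five-year data would exist for about one sixth of patients (9 of 56; 8 to 10 across the stated accrual rates). Failure and survival estimates would be valid but imprecise at five years. The crude late-toxicity rate would be biased low as an estimate of five-year risk.

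The follow-up counts assume uniform accrual and no loss to follow-up. The 5.9% figure rests on an assumed 10% risk and constant hazard; it shows direction and rough size only. The conclusion about the analysis is conditional on month 72 being the cut-off, which the text suggests but does not state. The sample size and the primary test stand. This should be corrected, but it does not threaten the main result.

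**What to change.** 1. In the Study Summary, 3.1 and 7.2, separate accrual (about 72 months; 67 to 88.5 months at 8 to 10 patients per year) from total duration to the last five-year visit (about 132 months; about 127 to 148.5). Say whether the inquiries in years 5 to 15 lie outside that duration.
2. In 7.1.2, replace the undefined end of study with a cut-off for each endpoint: lethargy once the last evaluable patient passes day 21; acute toxicity once the last patient passes day 90; final late-toxicity, relapse and survival results after the last patient's five-year visit. Label any earlier summary as interim and report it with median follow-up and numbers at risk. Also tie the quality-of-life summary to a named visit.
3. In 7.1.4, estimate late toxicity by cumulative incidence, with death as a competing event, instead of a crude proportion.

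The cost is wording in five places and one change of estimator, from a family of methods the plan already uses. No visits are added, because 6.2 already schedules five years. If waiting for the last five-year visit is thought too long, a stated minimum follow-up for a labelled earlier report would serve, provided it is fixed in advance.

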## **8 Safety and Adverse Events**

The investigator or research staff will be responsible for detecting, documenting and reporting all events that meet the definition of an adverse event (AE) or serious adverse event (SAE) as defined in this protocol.

### 8.1 Definitions

#### 8.1.1 Adverse Event

- An AE is any unfavorable and unintended symptom, sign (including abnormal laboratory findings), illness/disease (new or exacerbated), or experience that develops or worsens in severity temporally associated with the use of the investigational agent/device/procedure.

Intercurrent illnesses or injuries should be regarded as adverse events. Abnormal results of diagnostic procedures are considered to be adverse events if the abnormality:

- Results in study withdrawal.
- Is associated with a SAE.
- Is associated with clinical signs or symptoms.
- Leads to additional treatment or to further diagnostic tests.
- Is considered by the investigator to be of clinical significance.
- AEs are not to include:
  - Medical or surgical procedures (e.g. endoscopy, appendectomy); the condition leading to the procedure is an AE.
  - Situations where an untoward medical occurrence did not occur (elective and/or convenience admission to a hospital).
  - Anticipated day-to-day fluctuation of pre-existing disease(s) or condition(s) present or detected at the start of the study that do not worsen in grade or severity.
  - The disease/disorder that is being studied, or expected progression, signs, or symptoms of the disease/disorder being studied, unless more severe than expected for the subject's condition.

#### 8.1.2 Serious Adverse Event

- Adverse events are classified as serious or non-serious. An **SAE** is any medical occurrence that at any dose and:
  - Is fatal.
  - Is life-threatening.
    - Note: the subject was at risk of death at the time of the event, not an event that hypothetically might have caused death if it were more severe.
  - Required hospitalization or prolongs hospital stay (hospitalization signifies, in general, that the subject has been detained [at least an overnight stay] at the hospital or emergency department for observation/treatment that would not have been appropriate in a physician's office or outpatient setting).
    - Note: hospitalization for elective treatment, diagnostic purposes or a pre-existing condition that did not worsen from baseline is not considered an AE or SAE. Hospitalization/prolong hospitalization to allow for study efficacy assessment is not an SAE.
  - Results in persistent or significant disability or incapacity.
    - Note: a substantial disruption of a person's ability to conduct normal life functions. This is not intended to include experiences of relatively minor medical significance such as uncomplicated headache, nausea, vomiting, diarrhea, influenza, accidental trauma (e.g. sprained ankle) which may interfere or prevent everyday life functions but do not constitute a substantial disruption.
  - Lead to a congenital anomaly or birth defect.
  - Result in an important medical event.

#### 8.1.3 Clinical Laboratory and Other Safety Assessments

- Any abnormal laboratory test result (e.g. hematology, clinical chemistry, urinalysis) or other safety assessment (e.g. ECGs, radiological scans, vital signs), including those that worsen from baseline and are felt to be clinically significant in the medical and scientific judgment of the investigator are to be recorded as AE or SAEs if they meet the definition of an AE, as

defined above. However, any clinically significant safety assessments that are associated with the underlying disease, unless judged by the investigator to be more severe than expected for the subject's condition, are not to be recorded as AEs or reported as SAEs.

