Despite reductions in radiation doses and treatment fields, surveillance has emerged as an alternative and increasingly utilized adjuvant course. Approximately 15% to 20% of unselected patients with stage I seminoma who undergo surveillance following orchiectomy develop disease recurrence (35-43). As greater than 80% of these relapses occur in the para-aortic lymph nodes, deferring immediate adjuvant therapy and administering chemotherapy or radiation therapy upon relapse allows for successful salvage therapy in most patients, with equivalent overall survival rates as for patients receiving immediate adjuvant therapy (41-43). However, treatment of patients undergoing surveillance who relapse is usually more intensive and associated with increased morbidity (44-45). More recently, groups have advocated a risk-adapted management strategy to guide adjuvant therapy (46). As the risk of relapse is higher in patients with tumor sizes great than 4 cm, rete testis invasion, or pT3 or pT4 disease, in the absence of a contraindication to adjuvant therapy, only patients with pT1 or pT2 histologies and smaller tumors who are committed to long-term follow-up are ideal candidates for surveillance (8, 33, 43, 46).

Short-course adjuvant carboplatin for one or two cycles has emerged as an alternative to adjuvant radiation therapy or surveillance (8, 47-48). An MRC and European Organization for Research and Treatment of Cancer trial (MRC/EORTC ISRCTN27163214) randomized 1,447 patients with pT1 to pT3 stage I seminoma to one course of carboplatin or adjuvant radiotherapy to 20 Gy to 30 Gy in 200 cGy daily fractions primarily to the para-aortic region (16-17). At a median follow-up of 6.5 yrs, there was no difference in 5-year relapse-free survival rates between the carboplatin arm and the radiation therapy arm (94.7% vs. 95.5%, HR 1.25, 90% CI 0.83 to 1.89). Patients in the carboplatin arm had higher rates of Grade 1 or Grade 2 thrombocytopenia (12% vs. 2%,  $p<0.0001$ ) and Grade 3 or Grade 4 thrombocytopenia (4% vs. 0%,  $p<0.0001$ ), whereas patients in the radiation therapy arm had higher rates of dyspepsia (17% vs. 8%,  $p<0.0001$ ) and a trend towards increased lethargy and time off of work in the acute setting. Additionally, fewer new contralateral testicular germ cell cancers were observed in the carboplatin arm (0.2% vs. 1.2%, HR 0.22,  $p=0.03$ ).

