### **2.3 Phase II Secondary Objectives**

- 2.3.1 To evaluate the treatment efficacy of proton radiotherapy for all enrolled patients with seminoma as evidenced by time to local failure, time to distant failure, relapse-free survival, cause-specific survival, and overall survival, according to patient clinical stage and radiotherapy target volume treated.
- 2.3.2 To determine the incidence of additional acute toxicities of proton radiotherapy in patients with stage I, IIA, and IIB seminoma, including the incidence of hematologic toxicities, dyspepsia, and patients reporting being unable to perform normal work.
- 2.3.3 To assess late complications from irradiation to the para-aortic and pelvic regions using proton beam therapy, including late gonadal toxicity/spermatogenesis depression and the rates of contralateral testicular germ cell tumors, secondary solid cancers, and hematologic malignancies.
- 2.3.4 To compare the dose distribution to target volumes and surrounding normal structures using Dose Volume Histograms generated from proton plans used to treat study participants and photon plans that will be generated for comparison purposes.
- 2.3.5 To evaluate multiple domains of quality of life before, during, and after radiotherapy, including patient-reported assessments of lethargy, work or daily activity impairment, nausea/emeisis, change in bowel habits, mobility, self-care, pain/discomfort, anxiety/depression, and sleep.

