#### 7.1.4 Statistical Analyses.

- Acute and Late Toxicity: All acute and late toxicities will be graded by CTC Version 4.0 and tabulated. Toxicity rates and 95% confidence intervals will be calculated.
- Analysis by Radiation Therapy Type: all subjects enrolled in this study will be followed and assessed for all endpoint analyses. However, a separate analysis may be performed for subjects who were treated with photon therapy as a portion of their planned course of radiation therapy.
- Moderate to Severe Lethargy: The 3-week rate and 95% CI will be computed. A one-sample one-sided chi-square test will be performed to test the null hypothesis that the lethargy rate is 35% (same as photon) versus the alternative hypothesis that the rate is reduced to 20%. Patients must have a minimum of 21 days of follow-up to be included. As a secondary analysis, the 3-week lethargy rate and 95% exact CI will be computed for each disease stage. A Fisher's exact test will be employed compare these rates, to determine whether lethargy rates significantly differ by disease stage.
- Clinical Efficacy: Time to local failure and time to distant failure will be estimated by the cumulative incidence method within a competing risks framework (competing risks are local failure, distant failure, death). Relapse-free survival, cause-specific survival, and overall survival will be estimated by the Kaplan-Meier method. Median values and 95% confidence intervals will be calculated.
- Quality of Life: Longitudinal quality of life measurements will be examined by plots of mean $\pm$  SD over time. Repeated measures ANOVA or linear mixed effects models (to assess the impact of fixed effects covariates), will be used to analyze the repeated observations. Piecewise linear models may be required to fit non-linear trends, as expected for the initial decline and then gradual increase in quality of life measures.

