## 17 Appendices

### Appendix A: Common Terminology Criteria for Adverse Events, Version 4.0

Cancer Therapy Evaluation Program, Common Terminology Criteria for Adverse Events, Version 4.0, DCTD, NCI, NIH, DHHS  
May 28, 2009 (<http://ctep.cancer.gov>), Publish Date: June 14, 2010

Individual Category content listings are available to investigators at <http://ctep.cancer.gov>, with attention to the following System Organ Classes and CTCAE Adverse Events:

- **General Disorders and Administration Site Conditions:** Karnofsky Performance Score (not CTC but we would like to include/track), Fatigue, Weight Loss, Treatment Related Secondary Malignancy
- **Blood and Lymphatic System Disorders:** Anemia, Blood and Lymphatic System Disorders - Other, Specify
- **Gastrointestinal Disorders:** Nausea, Vomiting, Constipation, Diarrhea, Dyspepsia, Gastric Ulcer, Gastritis, Small Intestinal Obstruction:
- **Renal and Urinary Disorders:** Acute Kidney Injury, Hematuria, Renal and Urinary Disorders - Other Specify (Nocturia: # / Night), Urinary Frequency, Urinary Urgency, Urinary Incontinence, Urinary Retention, Urinary Tract Pain
- **Reproductive System and Breast Disorders:** Azoospermia, Erectile Dysfunction, Ejaculation Disorder:
- **Skin:** Pain of Skin, Skin and Subcutaneous Tissue Disorders - Other, Specify:

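### Hematologic toxicity (objective 2.3.2) has no definition, and no rule grades blood counts, so low-grade cytopenias may be under-counted

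*Combined protocol and SAP*

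**What the plan says.** Section 2.3.2 makes additional acute toxicities a secondary objective, "including the incidence of hematologic toxicities, dyspepsia" and inability to work among them. It sets no minimum grade and no definition for the hematologic part.

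Section 7.1.2 defines acute and late toxicity as Grade 3 or higher and non-hematologic, and section 8.2.2 refers to that definition. Section 7.1.4 says that all toxicities are graded by CTC version 4.0 and tabulated, and that "Toxicity rates and 95% confidence intervals will be calculated".

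The rules on what becomes an event are in section 8. Section 8.1.1 opens broadly: "An AE is any unfavorable and unintended symptom, sign (including abnormal laboratory findings), illness/disease (new or exacerbated"). It then narrows: "Abnormal results of diagnostic procedures are considered to be adverse events if the abnormality" meets one of five conditions. These are study withdrawal, association with an SAE, association with signs or symptoms, added treatment or further tests, or clinical significance in the investigator's view. Section 8.1.3 says of laboratory results that those which "are felt to be clinically significant in the medical and scientific judgment of the investigator are to be recorded as AE or SAEs", on condition that the AE definition is satisfied, which returns the reader to 8.1.1.

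In Appendix A the blood and lymphatic line reads "Anemia, Blood and Lymphatic System Disorders - Other, Specify".

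**The concern.** Section 8.2.1 lists hematologic depression among the common acute effects of radiation and says that acute effects are typically mild. The plan therefore expects mostly low-grade cytopenia. That is the class of event for which its recording rules depend most on one person's opinion.

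Thrombocytopenia is the only hematologic toxicity for which the protocol quotes rates (sections 1.1 and 7.1.3), yet it has no named term in the toxicity list. If two investigators differ on whether a mild platelet fall matters, the same laboratory value is an event at one proton center and not at the other. The reported incidence would then partly measure recording habits. At stake is the hematologic part of a descriptive secondary objective.

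**Working it through.** The plan states no figure that tests this point. Steps 1 and 2 set the rules side by side; steps 3 and 4 size the possible effect.

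**1. Follow one record.** A blood count taken during treatment shows platelets in the Grade 1 range. The patient has no symptoms, nothing is done, there is no SAE, and he stays on study.

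| Rule | Does it bring the value into the toxicity table? |
|---|---|
| 7.1.2 and 8.2.2, toxicity endpoints | No: Grade 3 or higher and non-hematologic only |
| 6.2.6 and 8.3, CTCAE grading | Only if the value is already an adverse event |
| 8.1.1, first four conditions | None is met |
| 8.1.1, fifth condition | Only if the investigator judges it significant |
| 8.1.3, laboratory results | Refers back to 8.1.1 |
| Appendix A | No platelet term; the open term can be used but is not prompted |
| 7.1.4, tabulation | Covers all toxicities, but does not say that a laboratory value alone is one |

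On the listed conditions, this record depends on the fifth alone. On the opening sentence of 8.1.1, it could be an event without any judgment. The text supports both readings.

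**2. When counts exist.** A baseline count is required. During treatment the weekly count is optional (section 6.1, note 8; section 6.2.4). For the eight weeks after treatment, section 6.2.5 lists only questionnaires. The first required post-baseline count is at the 90-day visit. Section 6.1 allows follow-up visits to move by 4 weeks, so that count may fall between day 90 - 28 = 62 and day 90 + 28 = 118.

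**3. Size.** Inputs: n = 56 (section 7.2); true Grade 1-2 thrombocytopenia rate p = 2% (radiation) or 12% (carboplatin), both from section 1.1. The share recorded, f, is an assumption shown over its whole range because the documents give none. Expected patients recorded = n x p x f, assuming that a count was taken in every patient.

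| f | p = 2% | p = 12% |
|---|---|---|
| 0 | 0 | 0 |
| 0.25 | 0.28 | 1.68 |
| 0.50 | 0.56 | 3.36 |
| 0.75 | 0.84 | 5.04 |
| 1 | 56 x 0.02 = 1.12 | 56 x 0.12 = 6.72 |

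The apparent rate is p x f. With f between 0.25 and 0.75, a true 2% appears as 0.5% to 1.5%, and a true 12% as 3% to 9%. At 2%, the chance of no case among 56 is 0.98^56 = 32% even with complete recording.

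**4. Extremes of the reported interval** (Clopper-Pearson, 95%). 0/56: 0% to 6.4%. 1/56 = 1.8%: 0.05% to 9.6%. 7/56 = 12.5%: 5.2% to 24.1%. At the radiation rate, losing the one expected case changes the report little. At 12%, losing all seven would change it materially.

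**The case against.** The strongest reply is that the plan does not exclude these events. Section 8.1.1 names abnormal laboratory findings inside the AE definition, and four of its five conditions need no judgment of significance. Section 8.1.3 can be read so that the significant results are merely an included subset. Appendix A has an open hematologic term, points to the full CTCAE listings and is not stated to be exhaustive. Toxicity assessment is scheduled separately (sections 6.1 and 6.2.6), and 7.1.4 says that all toxicities are tabulated. Section 8.5.1 refers to toxicity report forms and a manual of operating procedures that are not part of these documents.

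All of that stands against two stronger readings that a reader might infer: that a blood-count abnormality is recorded only if judged significant, and that only anemia can be recorded. The text supports neither, so low-grade cytopenias are at risk of being missed, not ruled out. The reply does not supply what is absent: a definition of hematologic toxicity for 2.3.2, or a sentence saying that counts are graded whatever the investigator thinks of them.

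It can also be said that optional testing is the larger cause of missed cytopenia. That is probably right, and it limits what the fix can deliver. It is a separate matter, because taking more counts would not settle whether a Grade 1 value is an event.

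**Conclusion.** The point holds as a gap in definition and ascertainment. Low-grade hematologic toxicity under 2.3.2 may be under-counted, and may be counted differently at the two treating sites. By how much cannot be determined: the share recorded could be anywhere from 0% to 100%. At the cited rates about 1 of 56 patients (2%) or about 7 of 56 (12%) is at stake. The 12% is a carboplatin rate and no patient here receives adjuvant carboplatin, so it serves only as an upper illustration. The 2% covers platelets only and comes from mainly para-aortic fields. Section 1.1 says that adding the pelvis raised hematologic toxicity but gives no rate, so 2% is not a ceiling either.

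A reader might infer that the reported proton rate will look better than the photon and carboplatin rates because those include asymptomatic cases. The documents do not support this. Section 1.1 does not say how the cited cases were found or whether they were asymptomatic, and section 7.1.4 plans no hematologic comparison.

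The change is worth making because it is cheap and removes a judgment-dependent step, but its reach is narrow. The primary endpoint is diary-reported lethargy, and the acute-toxicity stopping rule is non-hematologic; neither is affected.

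**What to change.** Add to section 7.1.4:

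> Hemoglobin, platelets, white cells, neutrophils and lymphocytes from every available post-baseline blood count are graded by CTCAE 4.0, irrespective of clinical significance or AE status. The worst grade through the 90-day visit, including its window, is tabulated with a 95% confidence interval among patients with at least one post-baseline count. The number of these patients and the timing of the counts are reported.

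Three points go with it:

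- Because the visit window reaches past day 90, where sections 6.2.6 and 7.1.2 begin to call events late, mark counts taken after day 90.
- State that on-treatment counts were optional. For the patients tested, the incidence is a lower bound because the lowest values may be missed. As a figure for all patients, it may also reflect who was tested. Do not present it as directly comparable with the cited photon or carboplatin rates.
- Add low platelet, white-cell, neutrophil and lymphocyte counts to Appendix A. Leave the AE and SAE reporting rules in section 8 unchanged.

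The cost is a short paragraph in 7.1.4, a few added terms and some programming. No extra blood tests or AE reports are needed. The reported incidence will be somewhat higher and will include asymptomatic findings, which should be said when it is presented.
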